8.4 Drug storage and supply

The IMP will be sourced by the Nottingham University Hospitals Clinical Trials Pharmacy via usual NHS supply chain. The IMP is not being manufactured specifically for use in this trial. IMP is supplied in white HDPE bottles. Catalent will supply the placebo in bulk. They will be stored and accounted for in Nottingham University Hospitals clinical Trials Pharmacy. The Nottingham University Hospitals Clinical Trials Pharmacy of a trial specific prescription signed by the PI or a prescriber delegated by the PI to prescribed study IMPs. The IMP and placebo can be stored at room temperature, and, must be consumed within 100 days of opening the bottle, which will be the date of dispensing. Unused IMP and placebo can be returned to the Nottingham University Hospitals Clinicals Clinical Trials Pharmacy for destruction as per their SOP.

8.5 Preparation and labelling of Investigational Medicinal Product

The Nottingham University Hospitals Clinical Trials Pharmacy will repack the active IMP into a new HDPE bottle, and package the placebo in matching HDPE bottles. IMPs will be labelled with the approved study label. Preparation and labelling of the investigational medicinal products will be completed in accordance with the exemption from the need for an MIA (IMP) (Regulation 37 of SI2004/1031 of the Clinical Trials Directive 2001/20/EC).

CONFIDENTIAL

Page 43 of 77

Nottingham University Hospitals

SHORT TITLE/ACRONYM Switch off gout attack study (SOG-AS) IRAS: 240464

Eudra CT number 2018-000963-99

8.6 Dosage schedules

Route: Oral

Frequency of administration: twice a day

Timing of each dose: with breakfast and with super

Maximum allowed each time a dose is taken: 2 capsules

Maximum duration of treatment of a subject: 28 weeks.

8.7 Dosage modifications

The dose of IMP or placebo can be reduced if the study participant develops an intolerance to the dose under investigation. They will be requested to reduce the dose to 2 capsules/ day in the first instance. After 3-5 days, they will be recommended to increase the dose to 3 capsules/day. If the study participant cannot tolerate 2 capsules/day, they will be allowed to reduce the dose to 1 capsule/day. The dose of study drugs will not be varied depending upon any laboratory results.

8.8 Known drug reactions and interaction with other therapies

Omega-3 fatty acids increase the prothrombin time and can increase the effect of anti-coagulants.

8.9 Concomitant medication

As omega-3 fatty acids can prolong prothrombin time, participants in the study should not be commenced on warfarin or any other anti-coagulant. If a study participant needs to commence on anticoagulation, then, they will be unblinded, and if on omega-3 fatty acids, this will be discontinued. Short course(s) of NSAIDs or colchicine (upto a maximum of 10 days at a time) can be prescribed to treat gout flares or other acutely painful conditions.

8.10 Trial restrictions

CONFIDENTIAL

Page 44 of 77

Eudra CT number 2018-000963-99

There are no contraindications whilst on the active phase of the trial including dietary requirements/restrictions. Women of childbearing potential (defined as having menstrual periods, perimenopausal or within 12 months of cessation of menstrual periods) are required to use adequate contraception for the duration of the trial and for 28 days after the completion of the trial. This includes:

- Intrauterine Device (IUD)
- o Hormonal based contraception (pill, contraceptive injection etc.)
- Double Barrier contraception (condom and occlusive cap e.g. diaphragm or cervical cap with spermicide)
- True abstinence

There is no need to adopt contraception for male participants.

8.11 Assessment of compliance

Returned capsule count of the IMP or placebo will be used to monitor compliance at week 14, and week 28. This will be recorded in the CRF. As this is a feasibility study, participants who are able to take fewer than 4 capsules/day will continue in the study, as, one of the study objectives is to assess compliance with study drugs. Compliance will be reported to the sponsor at study end. Participants will be advised to take the IMP or placebo capsules with food to increase compliance. Due to the theoretical possibility of the IMP and placebo being slightly different in appearance, returned pill count at week 14 will be done by the trial coordinator, an individual who does not conduct the other research assessment visits.

CONFIDENTIAL

Eudra CT number 2018-000963-99

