	University of Bath, [name], UK
	Email: [contact]
	[name], Emeritus Professor of Rheumatology, The
	University of Edinburgh, [name], UK
	Email: [contact]
	[name] [name], Professor of Rheumatology,
	Division of Musculoskeletal & Dermatological Sciences,
	University of Manchester, [name], UK
	Email: [contact]

CONFIDENTIAL

Page 7 of 77

Eudra CT number 2018-000963-99

IRAS: 240464

STUDY SUMMARY

gout on initiating urate lowering treatment – feasibility study for a randomized controlled trial Switch off gout attack study (SOG-AS)
Switch off gout attack study (SOG-AS)
Phase 2
Randomised placebo controlled feasibility study
Age ≥ 18 years
Known to have gout
Willing to initiate or increase dose of urate lowering treatment
≥1 gout flare in previous 12 months
60
1:1
28 weeks
28 weeks for efficacy assessment, 32 weeks for safety
assessment
18 months
The objectives of this feasibility study are to assess:
[1] dropout rate,

CONFIDENTIAL

SHORT TITLE/ACRONYM Switch off gout attack study (SOG-AS)

IRAS: 240464

	[2] recruitment rate,
	[3] quality of data collection during acute gout,
	[4] choose primary outcome for the main randomized
	controlled trial,
	[5] calculate sample size for the phase-III randomized
	controlled trial,
	[6] explore if there is a preliminary signal that omega-3 fatty
	acids can prevent flares of gout,
	[7] to decide number of GP surgeries needed in the main trial,
	and
	[8] assess compliance with study drugs.
Investigational Medicinal Product	omega-3 fatty acid ethyl ester soft-gel capsules 1 gm,
	containing 840 mg of eicosapentaenoic acid and
	docosahexaenoic acid
Formulation, Dose, Route of	Soft-gel capsules, 1 gm x 4/day, oral administration
Administration	
Placebo	Olive oil 1 gm
Formulation, Dose, Route of	Soft-gel capsules, 1 gm x 4/day, oral administration
Administration	

CONFIDENTIAL

IRAS: 240464

Eudra CT number 2018-000963-99

FUNDING AND SUPPORT IN KIND

FUNDER(S)	FINANCIAL AND NON FINANCIALSUPPORT
	GIVEN
Arthritis Research UK, [name]	Study funder (Research Council UK member)
[name]	
[name]. Contact [name],	
Email: [contact]	
Nottingham City CCG, [name]	Excess Treatment Cost for omega-3 fatty acids
[name]	
Contact: [name]	
Email: [contact]	
Nottinghamshire County CCG, Duncan	Excess Treatment Cost for omega-3 fatty acids
[name]	
[name]	
Contact: [name]	
Email: [contact]	

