7.6 Baseline data

Baseline visit: The study participant will see a Research Metrologist at the baseline visit. We anticipate this visit to last for 60-90 minutes.

At this visit, the Metrologist will confirm willingness to continue on the study and then enquire about the age at first gout flare, number of flares in previous 12 months, collect information about the current medications, confirm data on co-morbidity collected in the screening questionnaire, assess previous gout treatment, conduct a targeted musculoskeletal assessment, and measure height, weight, and blood pressure.

The participant will complete the gout activity questionnaire and the short-form 36 version 2 quality of life questionnaire. Approximately 5 ml blood will be collected for measuring omega-3 fatty acids, and, if **CONFIDENTIAL** Page **38** of **77**

Eudra CT number 2018-000963-99

the participant agrees, approximately 10ml blood will be collected and stored for future research including genetic research.

The participants will be given a flare diary to collect information about the severity of flares of gout. The participants will be randomised prescribed and dispensed a 14 week supply of IMP or matching placebo. The participants will also be given a supply of urate lowering treatment (typically allopurinol 100 mg/day or febuxostat 80 mg/day if allopurinol is contra-indicated or has previously caused sideeffects) not to be started until the 5th week and a rescue pack containing prednisolone tablets 30 mg/day and omeprazole capsule 20 mg/day for 1 week to be taken during a gout flare. In case corticosteroids are contraindicated, the rescue pack will contain tablet Naproxen 500 mg twice a day. and omeprazole 20 mg/day for 1 week with. The participants will be specifically asked not to start urate lowering treatment until day 29. They will be contacted by phone, or text 2-3 days prior to day 29 as a reminder.

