7.7 Trial Assessment

Dose up-titration visit: After confirming continuing consent, information on the number of flares of gout since last visit, changes in medication, any side effects, will be collected. Bloods will be collected for measuring serum uric acid (upto 5 ml) every 2-3 weeks until Serum Uric Acid below ≤300 µmol/l. A bedside portable uric acid meter will be used to measure the serum uric acid, and a sample will be sent to the clinical pathology laboratories at Nottingham University Hospitals if the serum uric acid is ≤300 µmol/l to document reaching treatment target. Any completed gout flare diary will be collected. Once the results of serum uric acid are available, the dose of urate lowering treatment will be increased, and the next dose up-titration visit will be arranged. Rescue packs of prednisolone or Naproxen will be replaced. At the week 14 visit, participants will be given a fresh supply of IMP or matching placebo for 14 weeks, and any unused medicines will be collected. We anticipate the doseup titration visit to last for up to 30 minutes. Telephone appointments will be substituted during the restrictions on research visits placed in the COVID-19 crisis as face-to-face researchappointments are Page **39** of **77**

CONFIDENTIAL

Eudra CT number 2018-000963-99

not allowed. We will accept serum urate <360 micromol/L as an acceptable treatment-target during this period. However, face-to-face appointments will be restarted once this advisory is lifted and provided the participant is still in the study. Any IMP/placebo or any study drugs will be posted to the participants as required.

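### Section 8.11 assesses compliance by returned capsule count alone and does not link it to the Section 8.7 dose reductions, so advised reduction and missed doses cannot be told apart

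*Protocol*

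**What the plan says.** The Study Summary gives the regimen for both arms as "Soft-gel capsules, 1 gm x 4/day, oral administration". At baseline (Section 7.6) each participant is "dispensed a 14 week supply of IMP or matching placebo", and at week 14 (Section 7.7) "participants will be given a fresh supply of IMP or matching placebo for 14 weeks, and any unused medicines will be collected".

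Section 8.11 sets the compliance measure: "Returned capsule count of the IMP or placebo will be used to monitor compliance at week 14, and week 28". The count goes into the CRF. The section also states that "participants who are able to take fewer than 4 capsules/day will continue in the study, as, one of the study objectives is to assess compliance". It gives no expected count, denominator or cut-off, and does not refer to Section 8.7.

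Section 8.7 covers intolerance: "They will be requested to reduce the dose to 2 capsules/ day in the first instance". It continues: "After 3-5 days, they will be recommended to increase the dose to 3 capsules/day". For those who cannot manage 2 a day, "they will be allowed to reduce the dose to 1 capsule/day". It describes no step back to 4 a day.

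Section 7.9 names poor tolerability and poor compliance as two separate things, neither of them a reason for withdrawal. Compliance is objective (h) in Section 3.1 and a secondary outcome in Section 3.2. Section 10.3.3 summarises secondary outcomes by mean (SD) and n (%).

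**The concern.** A returned count measures how many capsules were not taken. It does not show why. Under Section 8.7 a surplus can arise because the participant did what the protocol advised, and Section 8.11 places intake below 4 a day within the compliance objective without separating that case from missed doses.

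The difference matters for the purpose of the study. If capsules come back because the dose was lowered for intolerance, the main trial has a question about the tolerability of the regimen. If they come back because doses were forgotten or skipped, it has a question about adherence support. The only tolerability outcome listed in Section 3.2 is withdrawal due to omega-3 side effects, while Sections 7.9 and 8.7 keep intolerant participants in the study at a lower dose. Among the listed outcomes, intolerance short of withdrawal would therefore show mainly as a lower capsule count, reported as compliance.

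**Working it through.** The protocol gives no figure for compliance, so there is none to reproduce. The check is capsule arithmetic.

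**Inputs**
- Full dose: 4 capsules a day (Study Summary).
- Supply: 14 weeks = 98 days, dispensed twice (Sections 7.6 and 7.7).
- Reduction path: 2 a day for 3–5 days, then 3 a day (Section 8.7).
- Assumption: each supply is exactly 4 a day with no overage, so 98 × 4 = 392 capsules per period and 2 × 392 = 784 over 28 weeks. The protocol does not give these counts.

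**Step 1. One count, two explanations.** Suppose 196 capsules are returned from a supply of 392, so 392 − 196 = 196 were taken.
- Advised 2 a day: 2 × 98 = 196 advised, and 196/196 = 100% taken.
- Advised 4 a day: 4 × 98 = 392 advised, and 196/392 = 50% taken.

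The return is identical, so the count cannot distinguish the two.

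**Step 2. A participant who follows Section 8.7 step by step.** Assume 14 days at 4 a day, intolerance on day 15, 4 days at 2 a day, then 3 a day for the remaining 196 − 14 − 4 = 178 days, with every advised capsule taken.
- Taken: 14 × 4 + 4 × 2 + 178 × 3 = 56 + 8 + 534 = 598.
- Against 4 a day: 598/784 = 76%.
- Against the advised dose: 598/598 = 100%.
- Returned: 784 − 598 = 186 capsules. A participant advised 4 a day who missed 186/4 = 46.5 full days of dosing would return the same number.

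**Step 3. Sensitivity to timing.** The length of the 2-a-day step hardly matters: 3 days gives 56 + 6 + 179 × 3 = 599 (76%), and 5 days gives 56 + 10 + 177 × 3 = 597 (76%). The start date matters more. Within one 14-week period, with 3 or 5 days at 2 a day:

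| Full-dose days before reduction | Capsules taken of 392 | Against 4 a day |
|---|---|---|
| 0 | 291 or 289 | 74% |
| 28 | 319 or 317 | 81% |
| 56 | 347 or 345 | 88% |

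All of these are 100% against the advised dose.

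**Step 4. What could separate them.** The missing quantity is the number of capsules advised, which needs the level and date of each change. Section 8.11 requires the count in the CRF but does not require that record. Section 7.7 asks in general about changes in medication and side effects, and nothing links the answers to the count. Under Section 8.11 the week 14 count is made by the trial coordinator, who does not conduct the other assessment visits.

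**The case against.** The strongest reply is that nothing in the protocol is misstated. Section 8.11 sets no denominator, threshold or compliant/non-compliant class. It is compatible with scoring against the advised dose, and the formula may sit in a statistical analysis plan that is not shown. Intolerance is not lost either: side effects and medication changes are asked about at up-titration visits, side effects are assessed at every visit from week 5 to week 28 (Appendix 2), known omega-3 side effects go into the CRF (Section 9.2), and Section 7.9 separates tolerability from compliance. The CRF is not shown and may already hold dose changes. Intake against the full regimen is also a legitimate feasibility measure. Finally, little depends on the result: compliance is descriptive, poor compliance is not a withdrawal reason, and the efficacy signal is analysed by intention to treat (Section 10.7).

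Much of this stands, and it limits the point. A reader might infer that the protocol classes a participant who follows Section 8.7 as non-compliant. It does not, because no such class exists and a 4-a-day denominator is only one reading. A reader might also infer that the count will show a false difference between arms, or reverse a true one. That depends on intolerance rates and adherence levels the protocol does not give. Nor can a distortion from visit timing be shown, since that would need a supply-based denominator with no overage.

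What the reply does not remove is the data requirement. A later analysis plan can choose a denominator, but it cannot reliably rebuild the advised dose and its dates from general questions about side effects and medication.

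**Conclusion.** The point holds as a gap between Sections 8.11 and 8.7. The only named compliance measure cannot, by itself, separate advised dose reduction from missed doses, and the protocol does not require the record that would allow it. This affects a stated objective and a secondary outcome.

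In size, a participant who follows the Section 8.7 path exactly could read from 74% to 88% of the full-dose count in a 14-week period for the start dates tried, and about 76% over 28 weeks with onset on day 15. These figures assume 392 capsules per supply, every advised capsule taken, and scoring against 4 a day. They show what one unexcluded reading would give; they are not results the protocol prescribes. How many participants would be affected is unknown, because the protocol gives no expected rate of intolerance.

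The consequence is limited to interpretation of compliance for the main trial. It does not touch the primary outcome. No view is taken on the dose-reduction rule itself.

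**What to change.** In Section 8.11, refer to Section 8.7 and require the date and advised level of each dose change to be recorded in the CRF. Then report by arm:

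1. Exposure to the assigned regimen: capsules taken / (4 × actual days from dispensing to return).
2. Compliance: capsules taken / capsules advised over the same days. Use this for objective (h).
3. n (%) with any advised dose reduction. Read this with (1) as information on tolerability.

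In the worked example, (1) gives 76% and (2) gives 100% for the participant who followed Section 8.7. Both give 76% for someone advised 4 a day throughout who took the same 598 capsules over the same 196 days.

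The cost is one extra CRF log entry per dose change and two extra summary rows, so slightly more data entry. It needs no extra visits, tests or participants and changes no dose rule. The record should be kept prospectively.

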8.12 Name and description of each Non-Investigational Medicinal Product (NIMP)

All participants in the study will be commenced on urate lowering treatment as per the national British Society for Rheumatology recommendations. They will be commenced on Allopurinol as the first line urate lowering treatment. If this is contra-indicated, or causes side-effects, participants will be commenced on febuxostat as recommended in the NICE technology appraisal number 164. Participants who are able to tolerate allopurinol or febuxostat, but are unable to achieve serum uric acid < 300 micromol/L at the maximum licensed dose will be commenced on Benzbromarone. These medicines are recommended for treating gout in the UK and represent standard of care. For participants already on urate lowering treatment at the time of trial entry, but with serum urate > 360 µmol/L, the dose of urate lowering treatment will be increased or alternative urate lowering treatment will be prescribed as needed. People developing gout flares will be treated with courses of oral prednisolone, or NSAIDs as per patient and physician preference.

9. SAFETY REPORTING

9.1 Definitions

Term	Definition							
Adverse Event (AE)	Any untoward medical occurrence in a participant to whom a							
	medicinal product has been administered, including occurrences							
	which are not necessarily caused by or related to that product.							
Adverse Reaction	An untoward and unintended response in a participant to an							
(AR)	investigational medicinal product which is related to any dose							
	administered to that participant.							

CONFIDENTIAL

IRAS: 240464

Eudra CT number 2018-000963-99

	The phrase "response to an investigational medicinal product" means						
	that a causal relationship between a trial medication and an AE is at						
	least a reasonable possibility, i.e. the relationship cannot be ruled out.						
	All cases judged by either the reporting medically qualified						
	professional or the Sponsor as having a reasonable suspected causal						
	relationship to the trial medication qualify as adverse reactions.						
Serious Adverse	A serious adverse event is any untoward medical occurrence that:						
Event (SAE)	results in death						
	is life-threatening						
	 requires inpatient hospitalisation or prolongation of existing 						
	hospitalisation						
	results in persistent or significant disability/incapacity						
	consists of a congenital anomaly or birth defect						
	Other 'important medical events' may also be considered serious if						
	they jeopardise the participant or require an intervention to prevent						
	one of the above consequences.						
	NOTE: The term "life-threatening" in the definition of "serious" refers						
	to an event in which the participant was at risk of death at the time of						
	the event; it does not refer to an event which hypothetically might						
	have caused death if it were more severe.						
Serious Adverse	An adverse event that is both serious and, in the opinion of the						
Reaction (SAR)	reporting Investigator, believed with reasonable probability to be due						
	to one of the trial treatments, based on the information provided.						
CONFIDENTIAL	Page 47 of 77						

CONFIDENTIAL

Page 47 of 77

IRAS: 240464

Eudra CT number 2018-000963-99

Suspected	A serious adverse reaction, the nature and severity of which is not							
Unexpected Serious	consistent with the information about the medicinal product in							
Adverse Reaction	question set out:							
(SUSAR)	• in the case of a product with a marketing authorisation, in the summary of product characteristics (SmPC) for that product							
Expected Serious	Nil							
Adverse								
Events/Reactions								

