9.3 Recording and reporting of SAEs AND SUSARs

The period of time over which AEs, ARs, SAEs, SARs and SUSARs must be recorded and reported is:

- For SAEs consent
- For ARs / SARs and SUSARs from 1st IMP dose.

As omega-3 fatty acid capsules take 28 days to have an anti-inflammatory effect, any SAEs will be monitored for 28 days after last treatment dose. If the CI becomes aware of any SARs or SUSARs after the active monitoring period end, he will still inform the sponsor.

In all cases SAEs and SARs will be reported to the Sponsor, unless they are known side effects of omega-3 fatty acids.

All **SAEs** occurring from the time of **written informed consent** until 28 days post cessation of trial treatment must be recorded on the appropriate Form and faxed to the Sponsor **within 24 hours** of the research staff becoming aware of the event. Once all resulting queries have been resolved, the Sponsor will request the original form should also be posted to the Sponsor and a copy to be retained on site.

For each **SAEs** the following information will be collected:

- full details in medical terms and case description
- event duration (start and end dates, if applicable)
- action taken

CONFIDENTIAL

Page **49** of **77**

IRAS: 240464

Eudra CT number 2018-000963-99

- outcome
- seriousness criteria
- causality (i.e. relatedness to trial drug / investigation), in the opinion of the investigator
- whether the event would be considered expected or unexpected.

Any change of condition or other follow-up information should be faxed to the Sponsor as soon as it is available or at least within 24 hours of the information becoming available. Events will be followed up until the event has resolved or a final outcome has been reached.

All SAEs assigned by the CI or delegate as both suspected to be related to IMP-treatment and unexpected will be classified as SUSARs and will be subject to expedited reporting to the Medicines and Healthcare Products Regulatory Agency (MHRA). The Sponsor will inform the MHRA, the REC and the Sponsor of SUSARs within the required expedited reporting timescales.

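### Sections 9.1 and 9.3 set inconsistent causality rules for serious reactions, so SAR and SUSAR status depends on which section is applied

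*Protocol*

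**What the plan says.** The definitions table in Protocol section 9.1 has separate entries for an adverse reaction (AR), a SAR and a SUSAR.

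- **AR.** Causality must be at "least a reasonable possibility, i.e. the relationship cannot be ruled out". Either of two parties can make the judgement: "All cases judged by either the reporting medically qualified" "professional or the Sponsor as having a reasonable suspected causal" relationship qualify.
- **SAR.** The event must be serious and, in the opinion of the "reporting Investigator, believed with reasonable probability to be due" "to one of the trial treatments, based on the information provided". The Sponsor is not named.
- **SUSAR.** The definition opens with "A serious adverse reaction, the nature and severity of which is not" consistent with the product information. It therefore starts from the SAR.

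Section 9.3 gives an operating rule of its own: "All SAEs assigned by the CI or delegate as both suspected to be related to IMP-treatment and unexpected will be classified as SUSARs", and these go for expedited reporting. The same section says: "In all cases SAEs and SARs will be reported to the Sponsor, unless they are known side effects of omega-3 fatty acids". It also has the CI inform the Sponsor of SARs or SUSARs that come to light after active monitoring has ended.

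**The concern.** A SAR would ordinarily be an adverse reaction that is also serious. Here the causality wording becomes more demanding, and one of the two judges drops out, at the point where the event is serious. The SUSAR then has two definitions: one passes through the stricter SAR and the other does not.

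SUSAR status carries several duties. It starts expedited reporting to the regulator and the ethics committee, notification of investigators, and unblinding for that purpose (sections 9.3 and 9.4). SAR or SUSAR status also defines what the CI must still pass on once the 28-day monitoring period is over. The protocol convenes no DMC and plans no interim analysis, so correct classification of individual cases is an important part of safety oversight, alongside the periodic review by the TSC.

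**Working it through.** No arithmetic applies. The check sets the rules side by side and runs test cases through them.

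**The rules**

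| Class | Where | Causality bar | Who judges |
|---|---|---|---|
| AR | 9.1 | relationship not excluded | reporting professional or Sponsor |
| SAR | 9.1 | reasonable probability | reporting Investigator |
| SUSAR | 9.1 | taken over from the SAR | taken over from the SAR |
| SUSAR | 9.3 | suspected | CI or delegate |

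The scope differs too. The AR entry refers to the investigational product, and the SAR entry to any of the trial treatments.

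**Test cases, each a serious and unexpected event**

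| Case | AR (9.1) | SAR (9.1) | SUSAR (9.1) | SUSAR (9.3) |
|---|---|---|---|---|
| A. Investigator holds a link to the IMP reasonably probable; CI suspects it | yes | yes | yes | yes |
| B. Link cannot be excluded but is not held reasonably probable; CI suspects it | yes | no | no | yes |
| C. Only the Sponsor suspects a link | yes | no | no | no stated route |

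The rules agree in case A. In case B the two SUSAR definitions give opposite answers for the same event. In case C the event is an adverse reaction on the Sponsor's judgement and meets a seriousness criterion, yet no definition takes it further. The causality item collected for each SAE under 9.3 is likewise the investigator's opinion.

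**Late events.** During active monitoring, 9.3 sends an SAE to the Sponsor without reference to causality. Afterwards its duty covers SARs and SUSARs, and section 9.9 requires IMP-related SUSARs to be reported however late they occur. A late case B is covered if the 9.3 SUSAR rule is used. It is not covered if staff apply the 9.1 definitions literally.

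**The case against.** The best defence is that 9.3 is the rule staff will work from, and it uses the lower bar. It goes straight from a suspected, unexpected SAE to a SUSAR. Section 9.1 lists no expected serious events, and section 9.2 takes the known product side effects out of the serious classes. Nearly every SAE that the CI suspects would therefore count as unexpected and be expedited. This stands, and it rules out one tempting reading: that a possibly related serious event is never a SUSAR in this trial. That holds only under 9.1. What remains is that 9.1 is the definitions section and says otherwise.

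A second defence is that SAEs reach the Sponsor within 24 hours whatever their causality, apart from known omega-3 side effects. This also stands on the 9.3 text, so a reader should not infer that such events go unreported during active monitoring. (Section 9.5 words the duty more narrowly for deaths; that is a separate matter.)

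Third, a reader might infer that an event suspected only by the Sponsor can never become a SAR or SUSAR. The documents do not go that far. Section 9.4 gives the Sponsor verification of SARs and SUSARs, and nothing bars it from upgrading an event. The accurate statement is that no route is written down.

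Finally, the protocol has no graded causality scale, so the distinction between possible and probable comes from loose wording. That is fair, but the two entries stand in the same table with different words and different judges, and staff have no instruction to treat them as equivalent.

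**Conclusion.** The inconsistency is real and should be corrected. Within 9.1, the AR and SAR definitions differ in threshold and in judge. Between 9.1 and 9.3, the two SUSAR rules disagree for a serious, unexpected event whose link is possible but not held reasonably probable. Sponsor-only suspicion has no stated route beyond an adverse reaction.

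The consequence is limited to SAR and SUSAR classification, the trigger for expedited reporting, and the duty to report late SARs. It does not amount to general non-reporting of serious events. It also leaves the trial's estimates untouched: no outcome in section 3.2 is a SAR or SUSAR count, and the sample size does not depend on one.

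No number of affected events can be given. The protocol states neither an SAE rate nor a split of SAEs by causality, so any count for the 60 participants would rest entirely on assumed inputs. The conclusion rests on reading the 9.1 definitions literally and on taking reasonable probability as a higher bar than a relationship that cannot be excluded.

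**What to change.** Two wording changes in section 9, using the protocol's own AR threshold:

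1. In 9.1, define a SAR as an adverse reaction that also meets a seriousness criterion. Causality is then judged on the AR threshold, by the investigator or the Sponsor.
2. In 9.3, define a SUSAR as such a SAR that is unexpected, with suspicion by the CI, a delegate or the Sponsor being sufficient.

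The late-reporting duties in 9.3 and 9.9 then follow the same rule without further edits. The cost is a short amendment and possibly a few more events that need expedited reporting.
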